#### 14.3.6 Trimmed Means

[figure not shown]
The trimmed means analysis uses a different estimand and follows the approach of Permutt and Li (2017) [3]. This method provides an exact test using all randomized patients that is very robust and does not require any modeling assumptions. The estimand of the primary analysis is the difference between treatment groups in mean FEV1 change from baseline at week 48 in the population of all randomized patients, including the patients who die or are re-transplanted and have no FEV1 measurement at week 48. The primary analysis implicitly models the FEV1 at week 48 for patients who died or were re-transplanted, which is somewhat unnatural. In the approach of Permutt and Li, all dropouts are considered to be failures and these patients are given a FEV1 value of zero at week 48. The exact imputed value does not matter, as long as it is worse than all values observed in patients with FEV1 measurements at week 48. The imputed value will be zero. The estimand is the between group difference in mean change from baseline in the percentage p subpopulation with the best FEV1 values at week 48. Typical choices for p are in the range of 50 to 90%, depending on the anticipated percentage of patients with an imputed low value. For this sensitivity analysis p = 70% will be used. The method is based on a permutation test for the null hypothesis that the outcome distributions at week 48 are equal. The variant of the method described in Section 4.3 of Permutt and Li (2017) that exploits the intermediate FEV1 values and covariates in the same way as the primary analysis will be used. The only requirement for this method is that it must be reasonable to consider the outcome of dropouts as worse than the lowest outcome of the completers. This is reasonable for dropout due to death or re-transplantation but may not always be reasonable for dropout due to other reasons. Therefore, imputation will be applied only in case of death, re-transplantation, or lack of efficacy IEs.

CCI			

Final Version 5.0 Page 50 of 76

[figure not shown]
CCI		
 		
	 	

[figure not shown]
CCI		
	1	
	_	
. = = =		
•====		

CCI
,

CCI		
	1	
_		

[figure not shown]

Final Version 5.0 Page 57 of 76

CCI

#### 14.6 SUBGROUP ANALYSES

Analyses of primary endpoints will be performed on the following subgroups of patients:

- Age class (<55 years, ≥55 years),

- Gender (female, male, undifferentiated),
- Region (North America, all other countries together),
- Severity of disease, defined by:
  - % of baseline FEV₁ over personal best FEV₁ post-transplant (baseline FEV₁ >80%,
     >65–80%,
     >50–65%,
     and ≤50% of personal best FEV₁ post-transplant),
  - baseline FEV1 % of predicted (<70%, ≥ 70%),

  - baseline FEV1/FVC ratio (< 0.7, ≥ 0.7),

  - BLAD at baseline (Yes, No);
- Race (American Indian or Alaskan Native, Asian, Black or African American, Native Hawaiian or Other Pacific Islander, White, Other),
- Use of azithromycin at randomization (Yes/No).

Final Version 5.0 Page 59 of 76

Subgroup levels may be pooled to have an adequate number ( $\geq 10$ ) of patients per strata to perform the analysis. Decision on pooling will be taken during the blinded DRM, before data base lock.

Within each subgroup level, descriptive analyses (section 8.1) will be performed on:

- FEV1,
- FEV1/FVC,
- Time to Progression of BOS.

FEV1 and FEV1/FVC change from baseline will be compared using a two-sample t-test (assuming unequal variances) or, if the required assumptions are not met, a two-sample Mann–Whitney U test.

Comparison of time to progression of BOS curves among treatments will be performed with the log-rank test.

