### 8.2 Sample Size Considerations

The initial sample size was based on the following considerations. Assuming a treatment group difference for mean FEV1 change from baseline of 200 mL (0.2 L) and a standard deviation of 350 mL (0.35 L) at the end of treatment Week 48, an independent samples t-test with a one-sided type I error level of  $\alpha$ =0.025 will have at least 80% power to reject the null hypothesis when the sample size in each treatment group is at least 50 patients. To compensate for a loss of power due to premature withdrawals, a total of 110 patients will initially be randomized.

An interim analysis (IA) was performed to re-assess sample size and delivered to the Sponsor on December 1st, 2021. Results of the IA are presented in a separate IA report (section 19.1).

It was anticipated that approximately 160-170 patients have been randomized in BOSTON-2 and approximately 60 patients in BOSTON-1. 169 patients were actually randomized in BOSTON-2 and 62 patients in BOSTON-1.

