### 14.1.3 Analysis Model

The primary efficacy analysis will be carried out using a LMM for repeated measurements, using all observed available  $FEV_1$  measurements. In case of death or re-transplantation events,  $FEV_1$  will be imputed as zero at each nominal day post event.

The dependent variables are the absolute change from baseline of FEV1 measurements at visit 2 (i.e., the first post-baseline visit) through visit 9 (Week 48). For the definition of baseline FEV1 please refer to section 8.1.1.

A flexible and robust model will be chosen for the random part of the LMM according to a prespecified stepwise procedure (see next section). The fixed part of the LMM is specified as follows: the model will contain (except from the intercept) time cubic splines, treatment, the interactions of time splines by treatment, baseline FEV1, the interactions of time splines with the baseline FEV1, region (North America versus all other countries together), age (< 55 versus  $\ge 55$  years), and use of azithromycin at randomization (i.e. Baseline, Visit 1).

The primary efficacy parameter will be estimated from the model by the adjusted difference between treatment groups in mean FEV1 change from baseline after 48 weeks. The p-value for the null hypothesis of no difference and a two-sided 95% confidence interval for the difference will be provided.

Superiority of L-CsA will be demonstrated by a statistically significant result (defined as p<0.025, one-sided) in favor of the L-CsA plus SoC treatment compared to SoC alone.

The above comparison between treatment groups at all the other visits (2-8) will also be presented.

A figure of observed mean change from baseline and standard errors at each visit, by treatment group will be presented. A figure with adjusted mean changes from baseline at each visit by treatment group derived from the LMM will be provided.

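### Subgroup analyses test treatment separately within each level and include no treatment-by-subgroup interaction, so they cannot show whether the effect differs between levels

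*SAP*

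**What the plan says.** SAP 14.6 lists nine subgroup factors: age, gender, region, four measures of severity (percent of personal best FEV1, percent predicted FEV1, FEV1/FVC ratio, BLAD), race, and azithromycin use at randomization. Before pooling they have 25 levels (2+3+2+4+2+2+2+6+2).

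Within each level the section announces descriptive analyses and then specifies between-arm tests. FEV1 and FEV1/FVC "change from baseline will be compared using a two-sample t-test (assuming unequal variances"), with Mann-Whitney U as the alternative, and time to BOS progression is tested by log-rank. On size, "Subgroup levels may be pooled to have an adequate number" of patients, set at 10 or more, with pooling decided at the blinded data review meeting. The section gives no covariates, significance level, interaction term or rule of interpretation.

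The primary analysis in SAP 14.1.3 is different. It is carried out "using a LMM for repeated measurements, using all observed available" FEV1 values, with baseline FEV1, region, age group and azithromycin use in the model. In the visible text of the SAP, treatment interacts only with time or visit. The visible protocol text plans no subgroup analysis, so SAP 14.6 is the only specification.

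**The concern.** A subgroup analysis asks whether the treatment effect differs between kinds of patient. A separate test in each level asks whether the effect is non-zero in that level, and the answer depends heavily on how many patients the level holds. If the true effect is the same everywhere, one level will often reach significance while the other does not. A reader of the resulting tables could conclude that the drug works in one age group, region or severity band and not in another when nothing supports that.

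The method also departs from the primary analysis. The t-test drops the model's covariates and the earlier visits. Section 14.6 does not restate how missing Week 48 values, or the zeros imputed for death and re-transplantation, enter the subgroup tests. If Mann-Whitney is used in some levels and not others, levels of one factor are no longer compared on the same scale.

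**Working it through.** **Inputs**
- Effect and spread (SAP 8.2): "change from baseline of 200 mL (0.2 L) and a standard deviation of 350 mL (0.35 L) at the end of treatment Week 48", so d = 200/350 = 0.571.
- Planned size (SAP 8.2): the t-test "will have at least 80% power to reject the null hypothesis when the sample size in each treatment group is at least 50 patients", and "a total of 110 patients will initially be randomized".
- Actual size (SAP 8.2): "169 patients were actually randomized in BOSTON-2 and 62 patients in BOSTON-1", so 169/2 = 84.5 per arm.
- Significance level: the primary claim needs a "statistically significant result (defined as p<0.025, one-sided") (SAP 14.1.3). Section 14.6 states none. I assume the same level, equivalent to 0.05 two-sided.
- Subgroup splits: not in the documents. I assume 50/50, 30/70 and 10/90, and that the tests are on Week 48 change.

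**1. The SAP's own figure.** n = 2(1.96 + 0.842)²/0.571², about 48.1, so 49 per arm. The exact t-test gives 79.96% power at 49 and 80.8% at 50. The planned 50 per arm reproduces. Allowing about 9% withdrawal, 100/0.91 is about 110.

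**2. Overall power now.** At 84.5 per arm it is 96%.

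**3. Separate tests, identical 200 mL effect in both levels.** The levels hold different patients, so P(exactly one significant) = p1(1 − p2) + p2(1 − p1).

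| Case (assumed) | Power in each level | Exactly one significant |
|---|---|---|
| 50/50, 42 per arm per level (exact t) | 0.735, 0.735 | 2 × 0.735 × 0.265 = 0.39 |
| 30/70 (normal approximation) | 0.530, 0.874 | 0.530 × 0.126 + 0.874 × 0.470 = 0.48 |
| 10/90 (normal approximation) | 0.216, 0.941 | 0.216 × 0.059 + 0.941 × 0.784 = 0.75 |
| 50/50, one third missing, 28 per arm per level (exact t) | 0.556, 0.556 | 2 × 0.556 × 0.444 = 0.49 |

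The normal approximation gives 0.38 for the first row. In a level at the permitted minimum of 10 patients (taken as 5 per arm), power is about 12%.

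**4. Interaction test instead.** It wrongly declares a difference in 5% of trials per factor. For N1 and N2 patients in the two levels, SE = 350 × √(4/N1 + 4/N2), and power for a true 200 mL difference between levels is Φ(200/SE − 1.96).
- 50/50: SE 107.7 mL, power 46%.
- 30/70: SE 117.5 mL, power 40%.
- 10/90: SE 179.5 mL, power 20%.

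**5. All nine factors.** I simulated 169 patients with a uniform 200 mL effect, nine independent two-level factors and Welch tests at two-sided 0.05.
- Separate tests: at least one factor significant in one level only in about 80% of trials (50/50) and 95% (30/70).
- Correlating the four severity factors (0.7, assumed) changes this little: 79% and 94%.
- Unadjusted interaction tests: at least one false interaction in 37% to 38%, in line with 1 − 0.95⁹ = 0.37.

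**The case against.** The strongest reply is that SAP 14.6 calls these analyses descriptive. They are outside the hierarchy in SAP 8.4, carry no alpha, and no subgroup claim is planned. That stands. A reader might infer that the trial's confirmatory error is inflated, or that the SAP intends to judge subgroup effects by comparing p-values. The documents support neither. But the section does plan between-arm tests within levels, and the label does not stop their results from being compared.

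Other stronger readings also fail:
- A reader might multiply across factors, 1 − 0.61⁹ = 0.99. That treats nine results as independent when all nine re-split the same patients and share one overall treatment estimate. Simulation gives about 80% for equal halves.
- A reader might take 67% as the Week 48 completer rate. SAP 8.3.3 reports only that interim completion was above 67% and fluctuated across visits, so the one-third-missing row is an assumption.
- It is too strong to say baseline and stratification are ignored. The outcome is change from baseline; age and region are constant within their own levels; and the screening FEV1 stratum is not a factor in the primary model either.
- It is too strong to say the subgroup tests have no overall reference. SAP 14.3.4 plans a whole-population t-test, with zeros for death and re-transplantation.

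An interaction analysis also has limits. Treatment-by-subgroup-by-time terms add about 10 fixed effects for a two-level factor, 30 for the four-level severity factor and 50 for race before pooling, in a model for which SAP 14.1.5 already foresees non-convergence.

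**Conclusion.** The point holds as a weakness of interpretation and reporting. As written, the subgroup analyses cannot show whether the effect differs between levels. With an identical true effect, they suggest a difference in about 39% to 48% of trials per two-level factor, and at least once over nine factors in about 80% to 95%. Interaction tests give 5% per factor and about 38% over nine. The log-rank comparisons share the same logical weakness; I have not quantified it for them.

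The figures rest on the SAP's planning effect and SD, 169 patients, two-sided 0.05, assumed 50/50 and 30/70 splits, and nine two-level factors. The primary result is untouched. This is a cheap improvement, not a flaw that threatens the trial's main conclusion.

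**What to change.** Amend SAP 14.6 as follows:
- For each factor, add subgroup, treatment-by-subgroup and the corresponding by-time terms to the primary LMM.
- Pre-specify a simpler fallback if the model does not converge. One option is a Week 48 ANCOVA with treatment-by-subgroup, adjusted for baseline FEV1, with the same zero imputation for death and re-transplantation as the primary analysis.
- Show the Week 48 difference and 95% CI for each level in a forest plot, with the interaction estimate and p-value per factor. Drop within-level p-values.
- For time to BOS progression, use a model with an interaction term in place of separate log-rank tests.
- State that all subgroup results are exploratory, and that the lack of a significant interaction is not evidence of a uniform effect.

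The cost is SAP wording, standard code and a little more analysis work; no new data are needed. The downsides are possible convergence problems in small levels and low interaction power (about 20% to 46% for a 200 mL difference between levels). Emphasis should therefore fall on the intervals.

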#### 15 SAFETY DATA

#### 15.1 General Considerations

Summaries of safety data (e.g., AEs, laboratory data, vital signs) will be provided for the SAF. No inferential analyses are planned for safety endpoints.

### 15.2 Extent of Exposure

## 15.2.1 Exposure to L-CsA

Exposure to the investigational medicinal product (IMP), L-CsA will be confirmed based on the report of IMP vials returned and dosing recorded in the eCRF. IMP vials that were missing will not be included in the counts of returned (i.e. used) vials; this will also apply where vials are missing but the patients were considered to have taken the vials. A summary table will be prepared including the following details about administration of L-CsA:

- Descriptive statistics for the total vials planned. This is calculated as ([date of last dose date of randomization + 1] x 2 vials);
- Descriptive statistics for the total actual dose (mg). This is calculated as total empty (used) vials multiplied by dose;
- Descriptive statistics for the duration of treatment in days and weeks. For each patient, the treatment duration will be calculated as the difference between the dates of last and first administration of L-CsA plus 1;
- Descriptive statistics for the duration of treatment in days and weeks, excluding the inhalation temporarily discontinued. For each patient, the treatment duration will be calculated as the difference between the dates of last and first administration of L-CsA plus

Final Version 5.0 Page 60 of 76

1, excluding the days of any inhalation temporarily discontinued. Derivation: (date of last dose – date of first dose + 1) - (stop date of inhalation temporarily discontinued – start date of inhalation temporarily discontinued +1).

Compliance of L-CsA using the drug accountability data is calculated as the total empty (used) vials returned divided by the total vials planned and will be summarized on the FAS population. For the evaluation of compliance, all the planned vials up to the actual end of treatment for each patient will be considered in the calculation.

By-patient listings will present all IMP administration data.

### 15.2.2 Exposure to Study treatment (SoC or SoC+L-CsA)

SoC therapy period starts at randomization date and stops at date of study completion or early termination. L-CsA treatment period starts at date of first dose of L-CsA and stops at the date of last dose administered.

Descriptive statistics for the duration of any study treatment (SoC or SoC+L-CsA) in days and weeks will be provided. Since the SoC will cover the entire study period post-randomization, the study treatment duration (SoC or SoC+L-CsA) will be calculated as the difference between the date of study completion/early termination and randomization plus 1.

#### 15.3 Adverse Events

All AEs occurring during the clinical trial, whether or not attributable to study treatment, will be documented in the eCRF. All AEs will be coded to SOCs and PTs using the MedDRA dictionary (version 23.1).

Treatment-emergent adverse events (TEAEs) are defined as AEs with onset on or after the date of randomization.

The Investigator will assess the relationship (unrelated, possible, definite) of each AE to the clinical trial treatment assignment (L-CsA plus SoC or SoC alone). Treatment-related AEs are defined as events the Investigator considers to be possibly or definitely related to clinical trial treatment assignment.

All AEs reported in the eCRF will be presented in by-patient listings for the SAF.

The following summaries will be presented for AEs by treatment group and overall:

- Overview table including the number and percent of patients with:
  - o AEs,
  - o TEAEs.
  - o TEAEs leading to discontinuation of study treatment,
  - o TEAEs leading study discontinuation,

Final Version 5.0 Page 61 of 76

- o TEAEs leading to death.
- o TEAEs by severity (Mild, Moderate, Severe),
- o Study treatment related TEAEs,
- o Serious TEAEs,
- Serious study treatment related TEAEs;
- TEAEs, grouped within SOC by decreasing frequency of PT;
- TEAEs by decreasing frequency of PT;
- TEAEs leading to discontinuation of study treatment, grouped within SOC by decreasing frequency of PT;
- TEAEs leading to study discontinuation, grouped within SOC by decreasing frequency of PT;
- TEAEs leading to death, grouped within SOC by decreasing frequency of PT;
- TEAEs by maximum severity, grouped within SOC by decreasing frequency of PT;
- TEAEs by relationship, grouped within SOC by decreasing frequency of PT;
- Serious TEAEs, grouped within SOC by decreasing frequency of PT;
- Related serious TEAEs, grouped within SOC by decreasing frequency of PT.

Patients who have multiple events coded to the same PT or within the same SOC will be counted only once in the patient counts for the corresponding summaries, but all events will be considered and listed. Table presentations will contain counts of patients, percentages of patients, and the number of events.

Any AE with missing relationship will be assumed related and summarized in the possible related category to clinical trial treatment assignment. Patients who experience the same event multiple times will be included in the most related category for summarization.

In summaries including severity, the following severity categories will be summarized: 'Mild', 'Moderate', 'Severe'. Any AEs with missing severity will be assumed as 'Severe'. Patients who experience the same event multiple times will be included in the most severe category.

AE summaries will be ordered in terms of decreasing frequency for SOC, and PT within SOC, in the L-CsA plus SoC column.

The following by-patient listings will be provided:

- AEs:
- TEAEs;
- TEAEs leading to discontinuation of study treatment;
- TEAEs leading to study discontinuation;
- TEAEs leading to death;
- Study treatment related TEAEs;
- Serious TEAEs.

Final Version 5.0 Page 62 of 76

These listings will include at least: center, patient identifier, treatment group, AEs (SOC, PT, and verbatim term), AE start date/time, AE end date/time, duration of AE, severity, seriousness, action taken, outcome and relationship.

#### 15.3.1 Infections

All infections will be reported as AEs on the AE eCRF. The summaries described in this section will be provided for treatment-emergent infections (defined as for TEAEs). Treatment-emergent infections will be summarized on the basis of information reported on the AE eCRF.

For any infection, the following summaries will be presented by treatment group:

- Number (percent) of patients with at least one infection,
- Number and % of infections per patient (0, 1, 2, ...),
- Descriptive statistics for number of infections per patient.

The number of infections per patient and per patient-years (cumulative follow-up of each patient) will be provided by year (e.g., 2019, 2020, 2021, etc.) and overall.

A by-patient listing summarizing information on infections will be provided on SAF set.

### 15.3.2 Malignancies

All malignancies must be confirmed by histopathology. Malignancies are documented as AEs, and will be coded by SOC and PT. The summaries described in this section will be provided for treatment-emergent malignancies (defined as for TEAEs). Malignancies will be identified through a blinded medical review of collected AEs. The result of the medical review will be a flag for the identification of malignancies added in an excel sheet, that will be imported for analysis.

A summary table by SOC and PT and by-patient listing summarizing information collection will be provided on SAF.

## 15.4 Acute Tolerability of IMP

At Visit 1, acute tolerability of IMP (L-CsA) during initial dosing will be determined by measuring:

- Spirometry (FEV1, CCI , FVC) measured before and CCI
- Spontaneous report of cough or dyspnea, recorded as AE in the appropriate eCRF.

Descriptive statistics of pre-dose (V1), post-dose [CC] and and change from pre-dose will be presented for each spirometry parameter on the SAF population.

In addition, the number and percent of patients experiencing a decline of common in FEV1 will be presented.

Final Version 5.0 Page 63 of 76

The number and percent of patients experiencing new onset or worsening of TEAEs having the following PTs on the date of the first visit at which L-CsA is administered will be summarized:

- Cough;
- Dyspnea.

### 15.5 Clinical Laboratory Data

### 15.5.1 Hematology and Biochemistry

Clinical laboratory assessments will be performed at each visit by a certified local facility following the routine protocols at each site. As described in the clinical trial protocol (Section 13.1.5), the following clinical laboratory parameters will be reported in the eCRF:

### Hematology

- White Blood Cell (WBC) count with differential,
- Red Blood Cell (RBC) count,
- Platelet count,
- Neutrophils,
- Lymphocytes,
- Monocytes,
- Eosinophils,
- Basophils,
- Neutrophils Absolute Count,
- Lymphocytes absolute counts,
- Eosinophils absolute count,
- Basophils absolute count,
- Monocyte absolute count.

